## 14.2 Analysis Sets

Intent-to-Treat (ITT) Dataset: Includes all patients who are enrolled. The efficacy analyses will be performed using this dataset.

Evaluable Dataset: Includes all patients who are enrolled and received at least one dose of ENVARSUS XR and within targeted trough level of 3-9 ng/mL. In addition, the patients must have baseline and post-baseline conversion for at least one of the cognitive tests (without major protocol violation/deviation that would affect the cognitive measurement). The efficacy analyses will also be performed using this dataset.

Safety Dataset: Includes all patients who are enrolled and received at least one dose of ENVARSUS XR. The safety analyses will be performed using this dataset.

### **14.3 General Considerations**

#### **14.3.1 Definition of Study Days**

For the purpose of listing and summarizing data, time-in-study for each patient observation will be defined using study days. Study day is defined as the difference between the date of interest and the date of first dose of ENVARSUS XR. One day will be added if this difference is 0. The day prior to the first dose date is considered as “Study Day -1”. There is no “Study Day 0” for analysis purposes. In general, it is expected that enrollment date is the same date of the first dose date of ENVARSUS XR.

#### **14.3.2 Analysis Time Point**

Nominal visits will be used for analysis unless otherwise specified. No specific analysis visit window will be utilized for analysis purposes.

#### **14.3.3 Baseline Evaluation**

Patient demographics (including patient demographic survey) and baseline assessments will be summarized. Baseline evaluation is defined as the last non-missing evaluation prior to the first dose of ENVARSUS XR.

#### **14.3.4 Missing Data Handling**

Unless clearly specified, missing data will not be imputed for analysis; hence, in the summaries of continuous variables the sample size will be the number of patients with non-missing data; in the summary of categorical variables, patients with missing data will be excluded from the percentage calculation in general (with exception of demographic and baseline information).

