Visit 4 (Month 8± 30 days): Patients will be confirmed to have been on a stable dose of once-daily ENVARSUS XR before Visit 4 assessments are performed. Patients will take their morning dose of ENVARSUS XR and complete the following activities: PGI-I, WHODAS, PIRS-20, and cognitive outcomes assessments (listed above under primary and secondary endpoints). The physician will perform CGI-I. The continuation of ENVARSUS XR will be at the discretion of the patient’s treating nephrologist.

Early Withdrawal Visit: This visit should be scheduled as soon as possible for patients who withdraw from the study. Assessments of concomitant medication use, and AEs will be performed at this visit as well as all visit 3 assessments.

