**Analysis Methods:**

In general, continuous variables will be summarized with number of non-missing observations, mean, standard deviation (SD), median, minimum, and maximum displayed. Categorical variables will be summarized as counts and percentages.

The primary efficacy endpoint is the Global Composite Score on the RBANS. Raw scores on the RBANS will be age adjusted and converted into a series of Index Scores (reflecting domains such as immediate memory, delayed memory, attention, etc.) which will in turn be combined to generate the aforementioned Global Composite Score, a summary score reflective of overall neuropsychological status (scores have a mean of 100, SD of 15, impairment is typically defined as a score of <78 (1.5 SD below the mean). Descriptive summaries of patients' scores and percentiles at baseline (i.e., Visit 2) and post-baseline (i.e., Visit 3) will be provided. The mean change (absolute change) in -score the RBANS composite score from baseline to post-baseline will be evaluated using paired t-test at 0.05 significance level. A 95% confidence interval (CI) will be constructed for the mean change. Same methods will be used to analyze other cognitive test scores.

CGI-I and PGI-I will be summarized by number and percentages of patients in each category as well as combined categories of improvement (e.g., "Minimum improved", "Much improved", "Very much improved [CGI-I]/Very much better [PGI-I]").

Safety analyses (i.e., ENVARSUS XR exposure, adverse events, and trough level of ENVARSUS XR), as well as vital signs will be summarized descriptively.

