#### **10.1.6 Early Withdrawal Study Visits**

An early-withdrawal visit should be scheduled as soon as possible for patients who withdraw from the study. Assessments of concomitant medication use, and AEs will be performed at this visit. .

Patients who withdraw from the study will not be replaced. Follow-up will occur for any ongoing AEs at the time of withdrawal. The Investigator will be responsible for informing IRBs of the early termination of the study.

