## Study 2- Phase 2 Clinical Study in De Novo Kidney Transplant Recipients

Study 2 (NCT00765661) was an open-label Phase 2 study conducted in de novo kidney transplant patients randomized to once daily ENVARUS XR (N=32) or twice daily tacrolimus [immediate-release] capsules (N=31). The study was conducted in the US and patients received an organ from a deceased or living donor. Pharmacokinetics were evaluated during the first 2 weeks with an additional 50-week treatment and follow-up to evaluate safety and efficacy [see *Clinical Studies (14.1)*].

The starting dosage was 0.14 mg/kg/day (given once daily) for ENVARUS XR and 0.2 mg/kg/day (given twice daily) for tacrolimus [immediate-release] capsules. On Day 2 predose, the proportion of patients in the

ENVARSUS XR group with tacrolimus trough concentration that were within, above, and below 6 to 11 ng/mL was 53%, 11%, and 37%, respectively. The starting dose of 0.14 mg/kg/day in Study 2 formed the basis of dosing recommendations in de novo kidney transplant patients.

There were no deaths or graft failures in Study 2. Two patients in each arm discontinued due to adverse events. The most common adverse reactions included infections and cardiovascular events, and were generally similar to those reported in Study 1.

Study 3- Phase 3 Clinical Studies in Stable Kidney Transplant Recipients Converted from Tacrolimus Capsules  
In Study 3 (NCT00817206) stable kidney transplant patients were treated with ENVARSUS XR (N=162) or tacrolimus [immediate-release] capsules (N=162) and concomitant immunosuppressants in an open-label, randomized, multinational study [see *Clinical Studies (14.2)*]. The proportion of patients who discontinued treatment due to adverse reactions was 7.4% and 1.2% in the ENVARSUS XR and tacrolimus capsules treatment groups, respectively, through 12 months of treatment. The most common adverse reactions leading to discontinuation of study drug in the ENVARSUS XR treatment group was cardiac arrest (2 events).

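### The ITT analysis of RBANS is in effect complete-case: a patient with no Visit 3 score adds nothing to the mean change, and the scheduled early-withdrawal RBANS is given no role

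*Combined protocol and SAP*

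**What the plan says.** **Analysis set.** Section 14.2 defines the set as follows: "Intent-to-Treat (ITT) Dataset: Includes all patients who are enrolled. The efficacy analyses will be performed using this dataset". Section 14.5.1 requires the primary analysis on both the ITT and the Evaluable sets.

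**Test.** Section 14.5.1 compares RBANS at Visit 2 with Visit 3 but names no test. The test is named only in the synopsis, Analysis Methods, where the mean change "will be evaluated using paired t-test at 0.05 significance level".

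**Missing scores and visits.** Section 14.3.4 says that "missing data will not be imputed for analysis", with an opening exception for anything clearly specified. Section 14.3.2 says: "Nominal visits will be used for analysis unless otherwise specified". The only allowance given is one missing PIRS-20 item (section 14.5.2).

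**Early withdrawal.** The study design diagram gives an early-withdrawal visit to anyone who stops ENVARSUS XR before Visit 4. For its content:
- The synopsis, Study Visits, says that medication and AE assessments "will be performed at this visit as well as all visit 3 assessments".
- The Schedule of Study Activities marks RBANS and TMT in the early-withdrawal column, and section 8.3.1 refers to that schedule.
- Section 10.1.6 says: "Assessments of concomitant medication use, and AEs will be performed at this visit". It names no cognitive test.
- The discontinuation procedures under section 8.3.1 ask for every effort to complete the scheduled evaluations, then list only AEs and a medication review.

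**Visit 4.** RBANS is repeated at Visit 4 (section 10.1.4), but the only change from Visit 2 to Visit 4 among the endpoints is WHODAS (section 6.2.2).

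**The concern.** A paired t-test needs both scores. With no imputation and no rule that places an early-withdrawal score at Visit 3, the ITT and Evaluable analyses both omit every patient who lacks a Visit 3 RBANS. ITT then adds back only patients who have the scores but were excluded for trough level or a major deviation. It does not test whether the result depends on who stayed.

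That matters because stopping could depend on the outcome. The trial studies cognitive effects of tacrolimus, the plan allows withdrawal for an adverse reaction, and the appended label (Appendix 3, section 5.6) names discontinuation among the responses to neurotoxicity. There is one arm, so no comparator's drop-out can offset a bias, and section 10.1.6 says that withdrawn patients are not replaced. For someone who stops before Visit 3, the early-withdrawal RBANS may be the only post-conversion score. A site that works from section 10.1.6 alone may not collect it, and the plan does not say what to do with it if it is collected.

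**Working it through.** **1. The plan's own figure.** Section 14.1 gives effect size 0.5, 80% power, one-sided 0.025 and 34 evaluable patients. For a one-sample (paired) t-test with n - 1 degrees of freedom and noncentrality 0.5 x sqrt(n), power is 0.795 at n = 33 and 0.808 at n = 34. The 34 is reproduced.

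**2. Is it a power problem?** No. Section 14.1 enrols about 60 with 10% to 15% drop-out: 60 x 0.90 = 54 and 60 x 0.85 = 51. Power at an effect of 0.5 is 0.950 with 54 patients and 0.938 with 51. The issue is bias.

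**3. Who is in the estimate?**
- Visit 2 and Visit 3 scores present: included, even if the patient stops between Visits 3 and 4.
- Visit 2 and early-withdrawal scores only: no nominal Visit 3 score, so no change. The synopsis definition of the Evaluable set needs only a post-conversion score on one cognitive test, so on that criterion this patient could count as evaluable and still have no Visit 3 change.
- Visit 2 and Visit 4 scores, Visit 3 missed: no change.

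**4. Size of a possible bias.** Let p be the share without a Visit 3 score, 0.5 SD the mean change in those retained, and c the mean change in leavers.

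All-enrolled effect = (1 - p) x 0.5 + p x c. Overstatement = 0.5 / (all-enrolled effect) - 1.

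The 10% to 15% runs to end of study (Month 8), while the primary endpoint is at Month 4. The documents do not split it. Two assumptions are shown: half falls before Visit 3 (p = 5% to 7.5%), or all of it does (p = 10% to 15%).

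| p | c = 0: effect, overstatement | c = -0.5: effect, overstatement |
|---|---|---|
| 5% | 0.475, 5% | 0.450, 11% |
| 7.5% | 0.4625, 8% | 0.425, 18% |
| 10% | 0.450, 11% | 0.400, 25% |
| 15% | 0.425, 18% | 0.350, 43% |

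If c = 0.5, the overstatement is zero at every p.

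The SD of the RBANS change is not given. If it lies between 7.5 and 15 points (assumption), the worst-case difference of 0.05 to 0.15 SD is about 0.4 to 2.3 points.

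**5. Effect on the test, worst-case timing.** Suppose the all-enrolled mean change is zero and leavers average -0.5 SD. Those retained then average p x 0.5 / (1 - p): 0.056 SD at 10% (n = 54) and 0.088 SD at 15% (n = 51). With SD 1, the one-sided 0.025 test rejects in about 6% and 9% of trials.

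**6. Effect on a strong result.** With SD 1, a mean over all 60 is significant above about 0.258. If 54 retained patients average 0.5, the 6 leavers must average (0.258 x 60 - 0.5 x 54) / 6, about -1.9 SD, to lose significance. With 51 retained and 9 leavers the figure is about -1.1 SD. A true effect of 0.5 SD is robust; a small or null effect is where the choice matters.

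**The case against.** - **The drop-out is not all before Visit 3.** This stands. A reader might infer that all early stoppers vanish, but anyone with a Visit 3 score stays in, so the 11% to 43% range is a worst case.
- **The direction is assumed.** This stands. A reader might take the label as proof of upward bias: in its conversion study (Appendix 3, section 6.1, Study 3), "The proportion of patients who discontinued treatment due to adverse reactions was 7.4% and 1.2% in the ENVARSUS XR and tacrolimus capsules" groups respectively. Those figures cover 12 months and all adverse reactions. The reaction named as most often leading to discontinuation is cardiac arrest (2 events), and stopping is not linked to cognition. The label supports more stopping after conversion, not cognition-related stopping.
- **Visit 4.** A reader might say that ignoring Visit 4 RBANS is what loses the early stoppers. It is not: they leave through the early-withdrawal visit and have no Visit 4 score. Nor is the Visit 4 score wholly unused, since section 14.5.2 explores correlations among tests at each time point.
- **The early-withdrawal text.** Section 10.1 makes the schedule govern the procedures at each visit, and section 10.1.6 does not say that its list is complete. Section 10.1.3 likewise omits the physical examination and laboratory tests that the schedule marks at Visit 3. This is a mismatch to tidy, not a true conflict over what is required. It does not answer the missing analysis rule.
- **The study is exploratory and a full SAP is promised** before database lock (section 14). That lowers the severity and leaves room for a rule. A later SAP cannot recover tests that were never done.

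**Conclusion.** The point holds in this form: the ITT analysis of the primary endpoint is complete-case, and the early-withdrawal RBANS has no stated role in it. That the score goes unused is inferred from the plan's silence together with the nominal-visit rule; no sentence excludes it.

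The bias is possible rather than shown. Under the table's assumptions it is 5% to 18% with half the drop-out before Visit 3, 11% to 43% at worst, and zero if leavers resemble those retained.

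The documents do not support a case for replacing the primary test. A repeated-measures model assumes data missing at random, so it would not by itself answer a worry about informative drop-out. It belongs as a supportive analysis. This is a cheap improvement that should be made, not a fault that invalidates the design.

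**What to change.** 1. Align section 10.1.6 and the discontinuation list under section 8.3.1 with the schedule, so that RBANS and TMT are named at the early-withdrawal visit.
2. In sections 14.3.2 and 14.5.1 and in the synopsis, Analysis Methods, label the paired t-test as a complete-case analysis and report its n. Add an ITT analysis that takes the early-withdrawal RBANS as the post-baseline score for patients without a Visit 3 score, and report the time since last dose.
3. For changes still missing, add delta-adjusted or tipping-point multiple imputation, with zero change as one scenario. Do not fill in a single value of zero, which would shrink the variance artificially.
4. Add a supportive repeated-measures model on RBANS at Visits 2, 3 and 4, reporting the Visit 3 and Visit 4 changes from Visit 2. It mainly helps patients who miss Visit 3 but continue.

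**Cost.** Some text and a few extra analyses; every test is already in the schedule. An early-withdrawal score is taken as soon as possible after the last dose, so it may reflect much less than four months of exposure, or a patient already off drug. It should be read with that in mind. The estimate may also come out slightly smaller than the complete-case mean.

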### **14.4 Patient Population Summary**

Summary tables will provide frequency counts for patient disposition, including enrolled patients, treated patients, patients who completed Visit 4, and patients who discontinued early with reasons for discontinuation.

### **14.5 Efficacy Analysis**

#### **14.5.1 Primary Efficacy Analysis**

The primary efficacy endpoint is the Global Composite Score on the RBANS. Raw scores on the RBANS will be age adjusted and converted into a series of Index Scores (reflecting domains such as immediate memory, delayed memory, attention, etc.) which will in turn be combined to generate the aforementioned Global Composite Score, a summary score reflective of overall neuropsychological status (scores have a mean of 100, SD of 15, impairment is typically defined as a score of <78). Descriptive summaries of patients' scores and percentiles at baseline (i.e., Visit 2) and post-baseline (i.e., Visit 3) will be provided. The mean change (absolute change) in -score

the RBANS composite score from baseline to post-baseline will be evaluated at 0.05 significance level and analyses will be conducted based on both ITT and Evaluable analysis datasets.

#### **14.5.2 Secondary Efficacy Analysis**

Same methods as described above will be used to analyze other cognitive test scores or the global composite score of the Covid-19 Telephone Battery, should that be the primary outcome battery that we employ. In addition, the correlation among tests will be explored at each time point as well as the changes from baseline at Visit 3. Correlation coefficients and corresponding p-values will be displayed.

CGI-I and PGI-I will be summarized by number and percentages of patients in each category as well as combined categories of improvement (e.g., “Minimum improved”, “Much improved”, “Very much improved [CGI-I]/ Very much better [PGI-I]”).

PIRS-20 total score (sum of all 20 item scores with one missing item allowed) will be summarized at baseline and post-baseline visit. Absolute values at each time point as well as changes from baseline to post-baseline visit (i.e., Visit 3) will be analyzed.

All analyses will be based on ITT and Evaluable analysis datasets.

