### **6.2.2 Secondary Efficacy Endpoints**

The secondary efficacy endpoints include the following:

- Change in cognitive function from Visit 2 to 3 as measured by the following:
- TMT-A and TMT-B (visual scanning speed/visual attention)
- Change in QoL from Visit 2 to 3 and from Visit 2 to 4 as measured by the WHODAS
- PGI-I and CGI-I at Visit 3
- Change in quality of sleep from Visit 2 to 3 as measured by the PIRS-20

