#### **10.2.2.4 Pittsburgh Insomnia Rating Scale (PIRS-20)**

The PIRS-20 is the short version of the original PIRS, both copyrighted by the University of Pittsburgh. The original PIRS is a 65-scale item, widely used instrument in clinical and research practice. It was designed to rate the severity of insomnia in clinical trials and clinical practice. Domains of the PIRS-20 include subjective distress (12 items), subjective sleep parameters (4 items) and quality-of-life (4 items). The recall period of the PIRS-20 is the past 7 days. The PIRS-20 total score is the sum of all items and ranges from 0 (good sleep) to 60 (bad sleep). The PIRS-20 should be administered following the WHODAS at Visit 2 and Visit 3. Administration time: approximately 5-10 minutes.

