## 14.1 Sample Size

The study aims to enroll approximately 60 patients. With an expected drop-out rate of 10% to 15%, a maximum of fifty-two (52) evaluable patients are expected to reach the end of study.

In order to detect an effect size of 0.5 with 80% power and a one-sided type I error rate of 0.025, a sample size of 34 evaluable patients is needed. (NOTE: We simply need at least 34 patients to have adequate power, but we anticipate approximately having 52, meaning that this study will almost certainly NOT be underpowered). An interim analysis will be conducted when data are available for 17 (half of 34) evaluable patients, to better estimate the variation and effect of the treatment.

The rule for sample size adjustment is as follows:

Denote the planned sample size  $(n) = n_1 + n_2$ , where  $n_1 = 17$ ; and  $n = 34$  (i.e.,  $n_2 = 17$ ) Let

$r=1.5$  be the rate of adjustment (which leads to the maximum sample size of 52). Define

$N_{\text{new}}$  (final sample size) as

$$N_{\text{new}} = \begin{cases} n_1 + K, & n \leq N \leq rn \\ n, & N < n \\ rn, & N > rn \end{cases}$$

where  $K$  is the calculated additional required sample size (beyond first 17 evaluable patients) and  $N$  is the calculated total required sample size based on the observed change and variation from the interim analysis.

The range of possible total sample sizes based on the interim analysis is from 34 and 52, i.e., the sample size remains at 34 if the adjusted estimate is below 34, and increases to a maximum of 52 if the adjusted estimate is beyond 52.

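### The PIRS-20 scoring rule allows one missing item in a plain sum; read literally it scores a skipped item as good sleep, a small error that one sentence removes

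*Combined protocol and SAP*

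**What the plan says.** Three places in the combined protocol and SAP bear on the score.

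- Section 14.5.2 gives the scoring rule: "PIRS-20 total score (sum of all 20 item scores with one missing item allowed) will be summarized". It adds that "changes from baseline to post-baseline visit (i.e., Visit 3) will be analyzed".
- Section 10.2.2.4 describes the instrument. Its domains are "subjective distress (12 items), subjective sleep parameters (4 items) and quality-of-life (4 items"), and "The PIRS-20 total score is the sum of all items and ranges from 0 (good sleep) to 60 (bad sleep").
- Section 14.3.4 sets the default: "Unless clearly specified, missing data will not be imputed for analysis".

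Section 6.2.2 lists the measure among the secondary efficacy endpoints: "Change in quality of sleep from Visit 2 to 3 as measured by the PIRS-20". No section says how the total is computed when 19 of the 20 items are answered. There is no proration, item-mean substitution or rescaling rule for this scale.

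**The concern.** A sum is a safe score only when every item is present. Once a form with 19 answers is accepted and nothing is put in place of the gap, the total is short by whatever the missing item would have contributed. Zero is the good end of this scale, so the shortfall always makes sleep look better at the visit where the item was skipped. The change from Visit 2 to Visit 3 would then compare a 20-item total with a 19-item total for that patient.

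Three features of the study give this some weight. The PIRS-20 change is the only sleep endpoint. The design has one arm, with patients as their own controls (Section 7), so no concurrent group would absorb a difference in skipping between visits. And the shortfall tends to grow with the severity of insomnia, so the patients with the worst sleep would be mis-scored most.

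**Working it through.** **Inputs from the documents.** Number of items: 12 + 4 + 4 = 20, which agrees with the name of the scale and with 14.5.2. Range: 0 to 60, lower is better (10.2.2.4). Default: no imputation unless specified (14.3.4).

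**Assumptions.** The documents do not give the range of a single item. If all items have the same range, the maximum is 60/20 = 3 points. Skip rates and mean PIRS-20 totals are not given either, so ranges are shown.

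**The plan's own design figure.** Section 14.1 states the design target as "In order to detect an effect size of 0.5 with 80% power and a one-sided type I error rate of 0.025" and concludes that "a sample size of 34 evaluable patients is needed". A paired t-test (noncentral t) gives power 0.808 at n = 34 and 0.795 at n = 33, so 34 is reproduced. The point here does not depend on it; it only shows that a 10% skip rate would mean about 0.10 × 34 = 3.4 patients.

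**Step 1: which total do the passages produce from 19 answers?** There are three candidates.

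1. Add the 19 answers. This fits the sum, the allowance for one missing item and the no-imputation default. It equals a 20-item sum with the missing item set to 0.
2. Prorate or substitute. This is a form of imputation, so under 14.3.4 it would have to be stated, and it is not.
3. Set the total to missing. This conflicts with allowing one missing item.

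Only the first fits all the passages as written.

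**Step 2: error for one patient at one visit.** The loss equals the true score of the skipped item, 0 to 3 points. If that item is average for the patient, the loss is total/20, or 5% of the total:

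| True total | Sum of 19 answers | Loss | Prorated total (sum × 20/19) |
|---|---|---|---|
| 10 | 9.5 | 0.5 | 10 |
| 20 | 19.0 | 1.0 | 20 |
| 30 | 28.5 | 1.5 | 30 |
| 40 | 38.0 | 2.0 | 40 |
| 60 | 57.0 | 3.0 | 60 |

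With unchanged sleep and a complete Visit 2 form, a skip at Visit 3 gives a false change of 0 to −3 points (improvement). A skip at Visit 2 only gives 0 to +3 (worsening).

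**Step 3: effect on the mean change.** Bias = −(skip rate at Visit 3 − skip rate at Visit 2) × item score.

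- 10% at Visit 3 only, mean total 20: −0.10 × 20/20 = −0.1 points.
- 10% at Visit 3 only, mean total 40: −0.10 × 40/20 = −0.2 points.
- 5% to 20% at Visit 3 only, items worth 1 to 3 points: from −0.05 × 1 = −0.05 to −0.20 × 3 = −0.60 points.
- 10% at both visits, similar items: 0.
- 10% at Visit 2 only, item worth 1.5: +0.15 points.

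**Step 4: noise when skipping is balanced.** Suppose 10% skip at each visit, independently, and the item is worth 1.5. The added variance of the change is 2 × 0.10 × 0.90 × 1.5² = 0.405, an SD of about 0.64 points. The documents give no SD for the PIRS-20 change to set this against.

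**Step 5: what proration does not fix.** Take a true total of 20. If the skipped item was really 3, the answered sum is 17 and the prorated total is 17 × 20/19 = 17.9, an error of −2.1 against −3 for the plain sum. If it was really 0, the answered sum is 20 and the prorated total is 21.1, an error of +1.1 against 0. Proration removes the one-sided error for an average item; it does not recover the item.

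**The case against.** The strongest reply is that the plan nowhere says a skipped item scores zero. The allowance for one missing item can be read as a completeness threshold (19 answers make a form scorable), with the computation left open. Section 14.3.4 is a default rather than a prohibition, and the consequence it draws concerns how many patients enter a summary, not items within a questionnaire. Section 14 also promises a full SAP before database lock, and 10.2.2.4 rests the scoring on a cited source that may cover missing items.

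Much of this stands. A reader might infer that the plan scores skipped items as zero and rules imputation out; the documents do not support that as a statement of fact. The zero follows from a literal reading, and a rule stated for this scale would satisfy 14.3.4. What does not fall away is that no rule is stated. On the threshold reading the score for a 19-answer form is undefined, and two programmers could produce different totals. The reference does not settle it either: the citation number in 10.2.2.4 leads, in the reference list, to a memory-scale manual.

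A reader might also infer that the sleep result is biased toward benefit. That needs more skipping at Visit 3 than at Visit 2. The same form is given after the WHODAS at both visits, and nothing suggests unequal skipping. Nor does every skip cause an error: an item that would have scored 0 causes none. Insomnia is not an entry criterion, so mean totals below 20, with smaller losses, are plausible.

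**Conclusion.** The concern holds as a minor point. Followed as written, Sections 14.5.2 and 14.3.4 give a 19-item sum that puts the skipped item at the good-sleep end and lowers that visit's total by 0 to 3 points, about 5% for an average item. The sign of the false change depends on which visit has the gap. In the mean, only unequal skipping between visits leaves a bias, and under the assumed scenario (10% at Visit 3 only, mean totals of 20 to 40) it is 0.1 to 0.2 points. Balanced skipping leaves noise.

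The point range rests on equal item ranges; the group figures rest on assumed skip rates and totals. Neither is in the documents. The primary endpoint, the sample size and the safety analyses are untouched, and nothing here shows that a conclusion would change. The case for acting is that a better rule costs almost nothing and should be settled before anyone sees the scores.

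**What to change.** In Section 14.5.2, or in the SAP to be finalized before database lock, state: *PIRS-20 total = mean of answered items × 20 when at least 19 of 20 items are answered; otherwise missing.* Apply it at every visit where the scale is given, and name it as the specified exception to 14.3.4.

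The cost is one sentence and one line of code, with no new data. The downside is the assumption that the skipped item resembles the patient's average item. Setting any incomplete form to missing would also remove the ambiguity, but it would discard 19 answers and would mean dropping the allowance for one missing item.
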